### 7.2. Patient Exclusion Criteria:

- 1. History or presence of hair transplants.
- 2. Treatment with other medications or agents within 1 month of Screening or during the study that may affect hair regrowth or immune response, including but not limited to: corticosteroids administered orally, by injection, or applied to areas of skin affected by alopecia (intranasal and inhaled corticosteroids are allowed, eye and ear drops containing corticosteroids are also allowed); topical or oral retinoids; oral cyclines (minocin, tetracycline); platelet-rich plasma injections; topical application to affected areas of anthralin, squaric acid, diphenylcyclopropenone, or minoxidil; antimalarials.
- 3. Treatment with systemic immunosuppressive medications including but not limited to methotrexate, cyclosporine, and azathioprine; chloroquine derivatives; Janus kinase inhibitors (ruxolitinib, tofacitinib, etc) or etanercept within 3 months of Screening or during the study; or biologics (adalimumab, atlizumab, canakinumab, certolizumab, fontolizumab, golimumab, infliximab, mepolizumab, rituximab, secukinumab, tocilizumab, ustekinumab) within 6 months of Screening or during the study.
- 4. Active scalp inflammation, psoriasis, or seborrheic dermatitis requiring topical treatment to the scalp, significant trauma to the scalp, or other scalp condition that may interfere with the SALT assessment, or untreated actinic keratosis anywhere on the body at Screening and/or Baseline.
- 5. Known history of moderate to severe androgenic alopecia or female pattern hair loss prior to alopecia areata.
- 6. Unwilling to maintain a consistent hair style and hair style regimen, including shampoo and hair products (including hair dye, process, and timing to hair appointments), and to refrain from weaves or extensions throughout the course of the study, or shaving of scalp hair for 2 weeks preceding a SALT assessment.
- 7. Use of adhesive wigs, other than banded perimeter wigs, during the study.
- 8. History of a lymphoproliferative disease or malignancy, other than non-melanoma skin cancer or cervical carcinoma. Patients with 3 or more basal or squamous cell carcinomas diagnosed in the past 5 years are excluded.
- 9. Atypical nevi or cutaneous lesions that are suspicious for malignancy.
- 10. History of solid organ or hematological transplantation.

- 11. Fever, inflammation, or systemic signs of illness suggestive of systemic or invasive infection within 2 weeks prior to first dose of study drug.
- 12. Abnormal levels of thyroid stimulating hormone at Screening, defined as <0.9 x the lower limit of normal (LLN) and >1.2 x the upper limit of normal (ULN).
- 13. Screening labs outside the normal range for parameters associated with potential risk for treatment under investigation. This will include but is not limited to:
  - a. Platelets  $\leq 120 \times 10^9 / L \text{ or } \geq 600 \times 10^9 / L$
  - b. Absolute neutrophil count  $\leq 1.5 \times 10^9/L$
  - c. Hemoglobin levels  $\leq 11$  g/dL for females, or hemoglobin levels  $\leq 12$ . 5 g/dL for males
- 14. Screening blood glucose levels of hemoglobin A1c ≥6.5% (48 mmol/mol).
- 15. Abnormal liver function at Screening, defined as ≥1.5 × ULN of serum alanine transaminase, serum aspartate transaminase, serum alkaline phosphatase, or total bilirubin (unless isolated Gilbert's syndrome).
- 16. Abnormal renal function (estimated glomerular filtration rate <60 mL/min/1.73 m^2 using the MDRD equation) at Screening.
- 17. Subject has positive results for hepatitis B surface antigens (HBsAg), antibodies to hepatitis B core antigens (anti-HBc), or hepatitis C virus (HCV) at Screening.
- 18. Vaccination with herpes zoster vaccine or plans to receive a live attenuated vaccine during the study and up to 6 weeks or 5 half-lives (of the study product), whichever is longer, after the last study product administration.
- 19. Positive TB test, or history of incompletely treated or untreated tuberculosis.
  - NOTE: In cases where performance of a QuantiFERON-TB Gold test is not possible, testing with a Tuberculin Skin Test (TST) may be an option after consultation with the Medical Monitor. If the TST is negative, patients can be randomized into the study, assuming they meet all other inclusion and none of the exclusion criteria. If results are equivocal, or there is reason to believe the result is a false positive, a QuantiFERON-TB Gold must be performed before a subject is eligible for randomization.
  - NOTE: Subjects with documented completed treated with latent TB are not excluded.
- 20. History of prolonged QT syndrome or a Screening QTc interval with Fridericia's correction (QTcF) > 450 msec for males or QTcF > 470 msec for females.
- 21. History of alcohol, medication, or illicit drug abuse within 1 year before the first dose of study drug.
- 22. Females who are nursing, pregnant, or planning to become pregnant while in the study, and for 30 days after last dose of study medication.
- 23. Participation in another investigational study within the greater of 4 weeks or 5 half-lives of an investigational medication prior to screening or during the study.
- 24. Use of strong cytochrome P450 3A4 (CYP3A4) inhibitors (such as, but not limited to clarithromycin, conivaptan, grapefruit juice, indinavir, itraconazole, ketoconazole, lopinavir/ritonavir, mibefradil, nefazodone, nelfinavir, posaconazole, saquinavir, telaprevir, telithromycin, voriconazole, or fluconazole) dosed for systemic exposure.

- **Protocol CP543.2003** 
  - 25. Use of strong CYP3A4 inducers (such as, but not limited to barbiturates, carbamazepine, efavirenz, glucocorticoids, modafinil, nevirapine, oxcarbazepine, phenobarbital, phenytoin, pioglitazone, rifabutin, rifampin, St. John's Wort, or troglitazone) dosed for systemic exposure.
  - 26. Donation of blood > 499 mL of blood or plasma within 56 days of Screening (during a clinical trial or at a blood bank donation) and for 30 days after last dose of study medication.
  - 27. Patient has a known or suspected allergy to CTP-543 or any component of the investigational product.
  - 28. Subject has had major surgery within 8 weeks prior to Baseline or has a major surgery planned during the study.
  - 29. Subject has received any UV-B phototherapy (including tanning beds), has had psoralen-UV-A (PUVA) treatment, or excimer laser within 4 weeks prior to Baseline.
  - 30. Clinically significant medical condition or physical/laboratory/ECG/vital signs abnormality, psychiatric disease, or social condition, as determined by the Investigator, that may unfavorably alter the risk-benefit of study participation, adversely affect study compliance, or confound interpretation of study results.

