- 12. Abnormal levels of thyroid stimulating hormone at Screening, defined as <0.9 x the lower limit of normal (LLN) and  $\geq$ 1.2 x the upper limit of normal (ULN).
- 13. Screening labs outside the normal range for parameters associated with potential risk for treatment under investigation. This will include but is not limited to:
  - a. Platelets  $\leq 120 \times 10^9/L \text{ or } \geq 600 \times 10^9/L$
  - b. Absolute neutrophil count  $\leq 1.5 \times 10^9/L$

- CP543.2003, Amendment 2
  - c. Hemoglobin levels  $\leq 11$  g/dL for females, or hemoglobin levels  $\leq 12$ . 5 g/dL for males
- 14. Screening blood glucose levels of hemoglobin A1c ≥6.5% (48 mmol/mol).
- 15. Abnormal liver function at Screening, defined as ≥1.5 × ULN of serum alanine transaminase, serum aspartate transaminase, serum alkaline phosphatase, or total bilirubin (unless isolated Gilbert's syndrome).
- 16. Abnormal renal function (estimated glomerular filtration rate <60 mL/min/1.73 m^2 using the MDRD equation) at Screening.
- 17. Subject has positive results for hepatitis B surface antigens (HBsAg), antibodies to hepatitis B core antigens (anti-HBc), or hepatitis C virus (HCV) at Screening.
- 18. Vaccination with herpes zoster vaccine or plans to receive a live attenuated vaccine during the study and up to 6 weeks or 5 half-lives (of the study product), whichever is longer, after the last study product administration.
- 19. Positive TB test, or history of incompletely treated or untreated tuberculosis.
  - NOTE: In cases where performance of a QuantiFERON-TB Gold test is not possible, testing with a Tuberculin Skin Test (TST) may be an option after consultation with the Medical Monitor. If the TST is negative, patients can be randomized into the study, assuming they meet all other inclusion and none of the exclusion criteria. If results are equivocal, or there is reason to believe the result is a false positive, a QuantiFERON-TB Gold must be performed before a subject is eligible for randomization.
  - NOTE: Subjects with documented completed treated with latent TB are not excluded.
- 20. History of prolonged QT syndrome or a Screening QTc interval with Fridericia's correction (QTcF) > 450 msec for males or QTcF > 470 msec for females.
- 21. History of alcohol, medication, or illicit drug abuse within 1 year before the first dose of study drug.

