- Randomization/Day 1 may occur any time after Screening laboratory results are available and reviewed by the Investigator.
-  All subsequent visits and week increments should be based on the date of Visit 2. All visit windows are ±3 days for subsequent visits.
-  Also serves as the Early Termination Visit for patient withdrawal in this period.
-  The Safety Follow-Up Visit is intended for those patients who do not roll over into an openlabel extension and for patients who have been discontinued from the study and completed the Early Termination Visit (Week 24).
-  For females of childbearing potential, a serum pregnancy test will be performed at all visits aside from the randomization visit where a urine pregnancy test will be performed.

-  If PPD (skin test) is performed, subject will need to return to the clinic 24-48 hours after placement for PPD reading.
-  Includes hematology and serum chemistry.
-  When possible, collect pre-dose, except on Visit 11.
-  Will include thyroid stimulating hormone and hemoglobin A1c at Screening only.
-  Includes total cholesterol, low-density lipoprotein, high-density lipoprotein, and triglycerides.
- 11 Should be performed by the same rater, when possible, for the patient for the duration of the study.
-  For participants who authorize photographs to be taken of their scalp involvement and/or eye and nail involvement.
- Will be conducted at Visit 6 (Week 8) only.
- 14 Error! Reference source not found. Collection is ongoing.

2.	TABLE OF CONTENTS, LIST OF TABLES, AND LIST OF FIGURES			
1.	SYNOPSIS	7		
2.	TABLE OF CONTENTS, LIST OF TABLES, AND LIST OF FIGURES	16		
3.	LIST OF ABBREVIATIONS AND DEFINITIONS OF TERMS	21		
4.	INTRODUCTION	23		
4.1.	Overview of Alopecia Areata	23		
4.2.	Rationale for the Study	23		
4.2.1.	Scientific Rationale	23		
4.3.	Preclinical Information for CTP-543	25		
4.4.	Clinical Information	25		
4.4.1.	Clinical Studies of CTP-543	25		
5.	ETHICS	28		
5.1.	Institutional Review Board (IRB)	28		
5.2.	Written Informed Consent	28		
6.	STUDY OBJECTIVES	29		
6.3	Study Design	29		
6.4	Method of Treatment Assignment	30		
7.	SELECTION AND WITHDRAWAL OF PATIENTS	31		
7.1.	Patient Inclusion Criteria	31		
7.2.	Patient Exclusion Criteria:	32		
7.3.	Patient Withdrawal Criteria	34		
7.3.1.	Patient Withdrawal Procedures	34		
7.4.	Criteria for Study Termination	35		

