Patient safety will be monitored throughout the trial. The subject will be tested to ensure they do not have the Hepatitis B or C virus, thyroid function abnormalities or latent or active Tuberculosis, during the screening period. During the first 8 weeks of the Treatment Period, hematology and serum chemistry will be conducted every 2 weeks, followed by an assessment every 4 weeks thereafter through completion of the study at 24 weeks. Lipid levels will be assessed every 12 weeks throughout the Treatment Period. Significant cytopenias or other hematologic abnormalities will be managed by severity through dose interruption, or discontinuation, and signs and symptoms of infection will be closely monitored and treated promptly. Periodic skin examinations are recommended to detect non-melanoma skin cancers including basal cell, squamous cell and Merkel cell carcinoma. Patients who experience intolerable symptoms during treatment may discontinue the study at the discretion of the Investigator. Patients may withdraw consent at any time.

The Treatment Period will last 24 weeks to assess BID and QD doses, in parallel. Assessment of treatment response with SALT for efficacy will occur at 4, 8, 12, 16, 20 and 24 weeks.

Upon completion of the 24-week Treatment Period patients will be eligible to either complete treatment and exit the study following the safety follow-up visit, or roll-over into an open-label extension study.

Approximately 60 patients are planned to be enrolled in the study; approximately 30 patients per treatment arm.

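### Exclusion criterion 12 joins its low and high TSH limits with 'and', so read literally no Screening value can meet it

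*Protocol*

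**What the plan says.** The TSH rule appears twice in the Protocol, as exclusion No. 12.

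- **Section 7.2, No. 12:** abnormal TSH is "defined as <0.9 x the lower limit of normal (LLN) and >1.2 x the upper limit of normal (ULN".
- **Synopsis, Exclusion Criteria, No. 12:** "Abnormal levels of thyroid stimulating hormone at Screening, defined as <0.9 x the lower limit of normal (LLN) and", followed by an upper limit of 1.2 x ULN, here with a ≥ sign.

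The multiples (0.9 and 1.2) and the connector are the same in both places. Only the sign at the upper limit appears to differ.

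Section 6.3 gives the purpose of the test: "The subject will be tested to ensure they do not have the Hepatitis B or C virus, thyroid function abnormalities or latent or active Tuberculosis". On timing, a footnote to the schedule of events (Table 1) states: "Will include thyroid stimulating hormone and hemoglobin A1c at Screening only". Section 9.10 requires the investigator to use the Screening laboratory results to decide eligibility.

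Two other exclusions could bear on a thyroid finding. No. 13 begins "Screening labs outside the normal range for parameters associated with potential risk for treatment under investigation. This will include but is not limited to" and then lists platelets, neutrophils and hemoglobin, but not TSH. No. 30 covers a clinically significant condition or laboratory abnormality in the investigator's judgement.

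**The concern.** A two-sided laboratory exclusion has to catch a value that is too low or one that is too high. This one asks for a value that is both, so its literal meaning is the reverse of the purpose given in Section 6.3. The two copies share the fault, so neither corrects the other.

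This is an operative entry rule rather than background text. A site that applies the words strictly would let a patient with a markedly raised TSH past No. 12, while a site that reads for intent would exclude the same patient. TSH is scheduled at Screening only, so no later planned test would bring such a patient to light. At stake are uniform eligibility across sites and a clear answer to whether enrolling such a patient is a deviation.

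**Working it through.** The plan gives no figure to reproduce. The check is one of logic, with illustrative numbers.

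**Inputs.** The low limit is 0.9 x LLN and the high limit 1.2 x ULN (Synopsis and Section 7.2, No. 12). The documents give no TSH reference range, so the ranges below are assumptions.

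**Step 1: can both conditions hold?** For any reference range with 0 < LLN < ULN,

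0.9 x LLN < LLN < ULN < 1.2 x ULN.

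A value below 0.9 x LLN is therefore always below 1.2 x ULN, so the two conditions joined by *and* describe an empty set. This holds with > or with ≥ at the upper limit.

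**Step 2: numbers.** A fine grid of TSH values from 0 to 3 x ULN was tested against each wording, over four assumed ranges, the last almost degenerate.

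| Assumed LLN–ULN | 0.9 x LLN | 1.2 x ULN | Values meeting *and*, with > | Values meeting *and*, with ≥ | Under *or*, where > and ≥ disagree |
|---|---|---|---|---|---|
| 0.3–4.0 | 0.27 | 4.8 | 0 | 0 | 4.8 only |
| 0.4–4.5 | 0.36 | 5.4 | 0 | 0 | 5.4 only |
| 0.5–5.0 | 0.45 | 6.0 | 0 | 0 | 6.0 only |
| 1–1.0001 | 0.9 | 1.20012 | 0 | 0 | 1.20012 only |

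As an example, take the range 0.4–4.5 and a TSH of 3 x ULN = 13.5. It exceeds 5.4 but is not below 0.36, so the joint condition fails and the patient passes No. 12. A TSH of 0.1 also passes: it is below 0.36 but does not exceed 5.4.

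**Step 3: the sign.** With the limits read as alternatives, the two copies differ at one point, TSH = 1.2 x ULN, and nowhere else.

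**Step 4: do the other exclusions give the same rule?** No. 30 sets no numeric limit. No. 13 does not name TSH. If its general wording about values outside the normal range were applied to TSH, it would be stricter than No. 12. With the range 0.4–4.5, a TSH of 5.0 is above ULN but below 5.4, so No. 13 would exclude a patient whom the tolerance in No. 12 appears meant to admit. Neither exclusion reproduces the 0.9 and 1.2 limits.

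**Step 5: wording elsewhere in the list.** The platelet limits in No. 13a, also two-sided, are joined by *or*. The drafters therefore used the workable form in the very next criterion.

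**The case against.** The best defence is that nobody would apply the empty-set reading. The sentence speaks of abnormal levels in the plural and can be taken to list two abnormal ranges. Section 6.3 makes the purpose plain, and an investigator faced with a rule that no value can meet would see what was meant. That is probably how many sites would read it, and it limits the practical size of the problem. It does not make the text correct: an entry rule should not depend on each site inferring its connector.

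A reader might go further than the documents allow in three ways.

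- **That no patient could ever be excluded for a thyroid abnormality.** This is true only of No. 12 taken literally. No. 30 remains available, No. 13 arguably does, and Section 9.10 has the investigator review Screening results. A patient with TSH at 3 x ULN passes No. 12 but would not necessarily be enrolled.
- **That the upper limit itself differs between sections.** It is 1.2 x ULN in both. Only the sign differs, and a ≥ that lost its underline when text was extracted from the PDF would look the same. Other ≥ signs in the Section 7.2 list survive (Nos. 14 and 15), so the difference may be real, but it should be checked against the source file.
- **That the per-protocol set would vary by site.** SAP Section 7.2 has the Medical Monitor and sponsor classify deviations as minor or major centrally, before database lock. The per-protocol analysis is supportive and runs only if at least 10% of mITT patients have a major deviation (SAP Section 4.2). The main efficacy population is mITT (SAP Section 4.1), which this criterion does not define. The documents describe no programmed TSH check that would enforce the literal wording.

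**Conclusion.** The point holds as a drafting error in an operative eligibility rule. Under its literal wording, criterion 12 excludes 0% of possible TSH values in both places where it appears, for any reference range with LLN below ULN. This contradicts the purpose stated in Section 6.3. What is left is discretion under No. 30, or a contestable use of No. 13, so a fixed numeric limit gives way to one that can differ between sites. The apparent difference in sign is secondary and affects only a value exactly at 1.2 x ULN.

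The consequence is modest. Sample size and the primary analysis method do not change, and because patients are randomised after screening, the wording does not in itself bias the comparison of regimens. The number of patients affected cannot be estimated from the documents. The logical result needs no assumption about the reference range; only the numeric examples do.

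**What to change.** Reword criterion 12 in the synopsis and in Section 7.2 so that the low and high limits are alternatives, joined by *or* as in the platelet criterion. Use the same inequality sign at 1.2 x ULN in both places, with the sponsor stating which is intended. Send sites a short clarification so that all apply the same rule. If a TSH eligibility check exists in the eCRF, confirm that it matches.

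The cost is one word in two places, one sign and a site letter. The changes can go into the next amendment; the summaries of changes show that wording and typographical corrections have been handled that way before. If enrolment has already closed, the Screening TSH values of randomised patients can be compared with both limits before database lock. No new data, sample-size work or change to the SAP is needed.

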#### 7.3. **Patient Withdrawal Criteria**

All patients are free to withdraw from participation in the study at any time, for any reason, and without prejudice. The Investigator must withdraw any patient from the study if the patient requests to stop participating in the study. The Investigator, Sponsor, or its designee may remove a patient from the study at any time and for any reason if they believe the safety of the patient or the integrity of the data are at risk. In addition, patients should be withdrawn if they:

- Experience an intolerable adverse event
- Require a medication that is prohibited by the protocol
- Do not follow guidelines specified in the protocol (i.e., e.g. patient may be withdrawn if noncompliant with protocol procedures or study treatment administration)
- Any medically appropriate reason or significant protocol violation, in the opinion of the Investigator
- Are lost to follow up
- Female patient becomes pregnant

Patients who withdraw or are withdrawn from the study will not be replaced.

#### 7.3.1. **Patient Withdrawal Procedures**

A patient who prematurely discontinues study treatment/study participation should have all Week 24 assessments performed as an Early Termination Visit, and return for the Safety Follow-up Visit (See Table 1). The Safety Follow-Up Visit may be waived by the Sponsor in instances where patients have discontinued dosing prior to the Early Termination Visit on a case-by-case basis.

If a patient terminates early from the study, the Investigator will record the reason(s) for early termination on the relevant electronic case report form (eCRF). The specific reason for the withdrawal should be carefully documented on the eCRF.

Patients who require a dose interruption lasting more than 21 consecutive days for management of adverse events should be discontinued from the study. Adverse events resulting in patient early termination will be followed to the satisfactory resolution and determination of outcome, as ascertained by the Investigator (and/or Sponsor, or its designee); See Section 10 Adverse Events. The data will be recorded on the appropriate eCRF.

### 7.4. Criteria for Study Termination

There are no prospective stopping criteria for this study. The Sponsor reserves the right to discontinue the study at any time for clinical or administrative reasons.

Any termination required by the Sponsor must be implemented by the Investigator, if instructed to do so, in a time frame that is compatible with the patient's well-being.

#### 8. DESCRIPTION OF STUDY TREATMENTS

### 8.1. Description of Treatments

In the Treatment Period, patients will be stratified by alopecia areata subtype and randomized to 1 of 2 CTP-543 treatment arms in a 1:1 ratio. Treatments arms will include:

- CTP-543 12 mg BID (1 x 12 mg and 1 x placebo tablet every 12 hours)
- CTP-543 24 mg QD (2 x 12 mg in the morning and 2 x placebo tablets in the evenings)

### 8.2. Safety Criteria and Management for Stopping Doses

Patients who experience hematologic adverse events as described in Table 3 or adverse events that may reflect an unfavorable risk-benefit profile may have their dose interrupted or be discontinued from the study at the discretion of the Investigator. The Medical Monitor should be consulted whenever possible prior to decisions for dose interruption or patient discontinuation from the study.

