# Patients who require a dose interruption lasting more than 21 consecutive days will be discontinued from the study.

Patients who are discontinued from the study should undergo an Early Termination Visit and subsequent Safety Follow-up Visit as appropriate per Section 7.3.1 Patient Withdrawal Procedures, and associated adverse events followed as described in See Section 10 Adverse Events.

Hematology and serum chemistry parameters will be assessed every 2 weeks for the first 8 weeks of the Treatment, and every 4 weeks thereafter for the remainder of the study. Prior to dose interruption, hematology parameters should be confirmed with repeat testing at an interval deemed appropriate by the Investigator (e.g., at the next protocol-defined visit or an Unscheduled Visit), except in severe cases where immediate interruption of dosing is necessary for the safety of the patient. Blood draws confirming dose interruption criteria should occur prior to the first daily dose on the day of draw.

Dose interruption requirements for hematologic abnormalities are provided below. However, less significant changes may warrant clinical intervention and the Investigator should use his/her best clinical judgment when considering a dose interruption whether for singular or aggregate hematology results above the limits provided in Table 3, or for other clinical signs, symptoms, or considerations that suggest dose interruption is in the best interest of the patient.

Table 3: Selected Hematologic Thresholds for Dose Interruption

Neutrophil Count	Dose Adjustment		
Less than 1 x 10  /L	Interrupt dose until recovered to greater than $1.5 \times 10^9$ /L and resume dosing at previous dose		
Female Hemoglobin Level	Dose Adjustment		
Less than 10 g/dL	Interrupt dose until recovered to greater than 11.5 g/dL and resume dosing at previous dose		
Male Hemoglobin Level	Dose Adjustment		
Less than 11.5 g/dL	Interrupt dose until recovered to greater than 13 g/dL and resume dosing at previous dose		
Platelet Count	Dose Adjustment		
Less than 75 x 10  /L	Interrupt dose until recovered to greater than 75 x 10  /L and resume dosing at previous dose		
Greater than 750 x 10  /L	Interrupt dose until recovered to less than 600 x 10  /L and resume dosing at previous dose		

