Upon dose interruption, the parameters that triggered the interruption should be monitored at least weekly until either: 1) recovery above the threshold for dosing resumption is achieved, or 2) the allowable 21-day interruption has elapsed. In the case of severe neutropenia (neutrophil counts less than 0.5 x 10^9/L) patients should discontinue the study drug and receive instructions to seek medical help if they develop fever or signs of infection. Patients who discontinue the study due to lack of acceptable recovery of parameters within 21 consecutive day dose interruption period should continue to be monitored as appropriate through acceptable clinical resolution.

If the patient recovers above the threshold for interruption before the 21 consecutive day interruption period ends, they may remain in the study. Subsequent dose interruptions within a patient should be discussed with the Medical Monitor to determine continued participation in the study.

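### Protocol Section 8.2 makes action on a Table 3 blood count discretionary in one sentence and required in another, and its open-ended neutrophil row overlaps the instruction for severe neutropenia

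*Protocol*

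**What the plan says.** All the operative text is in Protocol Section 8.2.

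- **Opening paragraph.** Patients with the hematologic events in Table 3, or with other adverse events that suggest an unfavorable balance of risk and benefit, "may have their dose interrupted or be discontinued from the study at the discretion of the Investigator". The next sentence asks for the Medical Monitor to be consulted beforehand where possible.
- **Paragraph that introduces Table 3.** "Dose interruption requirements for hematologic abnormalities are provided below". It continues that "less significant changes may warrant clinical intervention and the Investigator should use his/her best clinical judgment" for results that have not reached the table's limits, or for other clinical reasons.
- **Table 3, neutrophil row, counts below 1 x 10^9/L.** "Interrupt dose until recovered to greater than" 1.5 x 10^9/L "and resume dosing at previous dose". The row has no lower limit and no cross-reference.
- **Text after Table 3.** For severe neutropenia, defined there as counts below 0.5 x 10^9/L, "patients should discontinue the study drug and receive instructions to seek medical help if they develop fever or signs of infection".
- **Last paragraph.** If the patient "recovers above the threshold for interruption before the 21 consecutive day interruption period ends, they may remain in the study". No exception is stated for counts that fell below 0.5 x 10^9/L.

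The outputs that depend on the action taken are in Protocol Section 11.4.4 and SAP Sections 13.1 and 13.2. They are treatment-emergent events leading to dose interruption, to study drug discontinuation and to study discontinuation, and potentially clinically significant laboratory values that led to interruption.

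**The concern.** A stopping rule should give a site one answer for one laboratory value. Here a site that relies on the opening paragraph may keep a patient on drug after a Table 3 limit is crossed. A site that relies on the paragraph above the table would interrupt. For the lowest neutrophil counts, the table taken alone leads back to dosing, while the sentence after it stops the drug. Patient safety is the main issue.

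The trial's answer is also touched. Comparing tolerability of the two regimens is part of the overall objective (Protocol Section 6), and some of the planned tolerability counts are defined by what the site did, not by what the laboratory found. If sites follow different sentences, those counts reflect site practice as well as the drug.

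**Working it through.** The plan has no figure to reproduce on this point, so the check is a comparison of text, one set argument and a simple scale calculation.

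**1. Do the two sentences cover the same events?** Yes. The opening paragraph names Table 3. The requirements sentence introduces Table 3, and the sentence after it refers to that table's limits. They cannot be assigned to different events.

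**2. Do they differ in force?** Yes. The opening paragraph is permissive and names investigator discretion. The later paragraph speaks of requirements, the rows are worded as instructions, and judgment is extended to less marked changes as something additional. If action at the limits were already discretionary, that extension would have nothing to contrast with.

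**3. Do the neutrophil instructions overlap?** Every count below 0.5 x 10^9/L is also below 1 x 10^9/L, so it meets both instructions:

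| Neutrophil count (x 10^9/L) | Table 3 row | Sentence after Table 3 |
|---|---|---|
| 0.5 to below 1 | Interrupt; resume at previous dose above 1.5 | Not addressed |
| Below 0.5 (for example 0.4) | Interrupt; resume at previous dose above 1.5 | Discontinue study drug |

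The sentence after the table does not say that it overrides the row, whether stopping is permanent, or whether it means leaving the study.

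**4. Does other text settle either point?** No. The Synopsis, Protocol Section 6.3 and SAP Section 3.1 say that significant cytopenias are managed by severity through interruption or discontinuation, without saying which applies when or whether it is mandatory. Protocol Section 7.3.1 gives only the 21-day limit.

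**5. Scale.** Inputs: about 30 patients per arm (Protocol Section 6.3) and 25 completers per arm (Protocol Section 11.1).

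- One patient handled differently changes an action-based percentage by 1/30 = 3.3 points.
- If k patients in an arm cross a limit, the number interrupted for that reason can lie anywhere from 0 to k, which is 0 to 3.3k points. For k = 3 this is 0 to 3/30 = 10.0 points. The documents give no expected k for this trial, so k is an assumption.
- The plan allows for 30 - 25 = 5 non-completers per arm. A patient who leaves the study under one reading and stays under the other uses one of them.

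**6. Direction.** Patients, investigators and site staff are blinded to regimen (Protocol Section 6.3, SAP Section 3.3), and the same text governs both arms. Randomization is described as stratified by alopecia subtype only (Protocol Section 6.4), so differing site practice can fall unevenly on the arms by chance. That is noise, and nothing in the documents gives it a direction.

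**The case against.** **The neutrophil sentence is a special case.** It names a narrower range and one action, and it follows the table. A careful reader would apply the specific sentence over the general row. This is a fair reading and makes the second conflict milder than the first. It does not remove it: the row has no floor, no text states the precedence, and the last paragraph on remaining in the study makes no exception. A reader might infer that the protocol directs such patients back to dosing. It does not; only the table row read alone leads there.

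**The Medical Monitor limits variation.** Section 8.2 asks for consultation where possible, and Section 9.10 sends clinically significant hematologic abnormalities that need intervention to the Medical Monitor. This reduces inconsistency between sites but does not say which sentence governs.

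**The confirmation step.** A reader might infer a further contradiction. Section 8.2 says "Prior to dose interruption, hematology parameters should be confirmed with repeat testing at an interval deemed appropriate by the Investigator", and the next protocol visit is one example given. After Week 8 visits are 28 days apart with windows of 3 days either side, so that visit could be 22 to 34 days away, against at least weekly testing and a 21-day limit once dosing is interrupted. The documents do not support calling this a contradiction. The same sentence offers an Unscheduled Visit, Section 9.11 names such visits for confirming hematology results, and severe cases needing immediate interruption are exempt. Confirmation before interruption and monitoring during it are different states. The long gap is permitted, not required.

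**The statistical effect is limited.** Overall adverse event incidence does not depend on the action taken, and SAP Section 13.2 tabulates treatment-emergent Grade 3 or 4 laboratory values by regimen regardless of action. This stands. The documents do not reproduce the grading limits, however, so they do not show whether those counts coincide with Table 3 crossings.

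**Few patients may be affected.** The dose rationale in Section 4.2 reports no interruptions for hematologic abnormalities to date at 12 mg BID. Section 4.4.1 reports three Grade 3 or 4 hematologic changes across the 4 mg, 8 mg and placebo groups. This suggests a small k. It is not decisive, because the 12 mg BID cohort was still ongoing and no 24-week patient data are given for 24 mg QD.

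**Conclusion.** The point holds on the current text. Section 8.2 gives action on a Table 3 crossing two different forces, discretionary and required. It also gives overlapping instructions for neutrophils below 0.5 x 10^9/L. The first conflict is the firmer; the second is literal but can be read as an unstated exception. Because the text concerns stopping doses, it should be corrected on safety grounds whatever the number of patients affected.

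The statistical consequence is modest: 3.3 percentage points per patient handled differently, confined to the action-based tolerability counts and resting on about 30 patients per arm and an unknown number of crossings. Two larger conclusions might be drawn, and neither is supported.

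- **Bias between the regimens.** Sites are blinded and both arms follow the same text, so the documents support between-site noise and no more.
- **Discretion as such costs the primary analysis its Week 24 data.** Protocol Section 7.3.1 asks for all Week 24 assessments at early termination, and SAP Section 6.3 carries forward missing SALT scores. A stop under a mandatory rule would have the same effect as a discretionary one.

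**What to change.** Reconcile the opening paragraph of Section 8.2, the paragraph introducing Table 3, Table 3 itself and the text after it, so that:

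- each laboratory value has one stated action, marked as mandatory or discretionary;
- the Table 3 neutrophil row and the severe-neutropenia sentence cover ranges that do not overlap, or one states that it overrides the other;
- the severe-neutropenia sentence says whether stopping is permanent and whether the patient leaves the study, and the last paragraph agrees with it.

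The medical team decides the content; no view is taken here on which rule is right.

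As an option, SAP Section 13.2 could add a count, by regimen, of patients who crossed a Table 3 limit whether or not dosing was interrupted. That gives a comparison on the protocol's own limits that does not depend on what sites did.

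The cost is a wording amendment in one section and, if the option is taken, one extra table from laboratory data already collected. The reconciliation itself needs no new visits or samples.
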